14.2.28 Data handling and programming rules

The following section should be used as guidance for development of the protocol, data handling procedures or programming requirements (e.g. on incomplete dates).

14.2.29 Study/project specific decisions

For each study (or project) various issues need to be addressed and specified in the protocol or RAP documentation. Any deviations from protocol must be discussed and defined at the latest in the RAP documentation.

The proposed primary analysis and potential sensitivity analyses should be discussed and agreed with the health authorities and documented in the protocol (or at the latest in the RAP documentation before database lock).

14.2.30 End of treatment phase completion

Patients **may** voluntarily withdraw from the study treatment or may be taken off the study treatment at the discretion of the investigator at any time. For patients who are lost to follow-up, the investigator or designee should show "due diligence" by documenting in the source documents steps taken to contact the patient, e.g., dates of telephone calls, registered letters, etc.

The end of treatment visit and its associated assessments should occur within 15 days of the last study treatment.

Patients may discontinue study treatment for any of the following reasons:

- Adverse event(s)
- Lost to follow-up
- Physician decision

- Pregnancy
- Protocol deviation
- Technical problems
- Subject/guardian decision
- Death
- Progressive disease
- Study terminated by the sponsor
- Non-compliant with study treatment
- No longer requires treatment
- Treatment duration completed as per protocol (optional, to be used if only a fixed number of cycles is given)

14.2.31 End of post-treatment follow-up (study phase completion)

End of post-treatment follow-up visit will be completed after discontinuation of study treatment and post-treatment evaluations but prior to collecting survival follow-up.

Patients may provide study phase completion information for one of the following reasons:

- Adverse event
- Lost to follow-up
- Physician decision
- Pregnancy
- Protocol deviation
- Technical problems
- Subject/guardian decision
- Death
- New therapy for study indication
- Progressive disease
- Study terminated by the sponsor

14.2.32 Medical validation of programmed overall lesion response

As RECIST is very strict regarding measurement methods (i.e. any assessment with more or less sensitive method than the one used to assess the lesion at baseline is considered UNK) and not available evaluations (i.e. if any target or non-target lesion was not evaluated the whole overall lesion response is UNK unless remaining lesions qualified for PD), these UNK assessments may be re-evaluated by clinicians at Novartis or external experts. In addition, data review reports will be available to identify assessments for which the investigators' or central reader's opinion does not match the programmed calculated response based on RECIST criteria. This may be queried for clarification. However, the investigator or central reader's response assessment will never be overruled.

If Novartis elect to invalidate an overall lesion response as evaluated by the investigator or central reader upon internal or external review of the data, the calculated overall lesion response at that specific assessment is to be kept in a dataset. This must be clearly documented in the

RAP documentation and agreed before database lock. This dataset should be created and stored as part of the 'raw' data.

Any discontinuation due to 'Disease progression' without documentation of progression by RECIST criteria should be carefully reviewed. Only patients with documented deterioration of symptoms indicative of progression of disease should have this reason for discontinuation of treatment or study evaluation.

14.2.33 Programming rules

The following should be used for programming of efficacy results:

14.2.34 Calculation of 'time to event' variables

Time to event = end date - start date + 1 (in days)

When no post-baseline tumor assessments are available, the date of randomization/start of treatment will be used as end date (duration = 1 day) when time is to be censored at last tumor assessment, i.e. time to event variables can never be negative.

14.2.35 Incomplete assessment dates

All investigation dates (e.g. X-ray, CT scan) must be completed with day, month and year.

If one or more investigation dates are incomplete but other investigation dates are available, this/these incomplete date(s) are not considered for calculation of the assessment date (and assessment date is calculated as outlined in [Section 14.2.25](#)). If all measurement dates have no day recorded, the 1st of the month is used.

If the month is not completed, for any of the investigations, the respective assessment will be considered to be at the date which is exactly between previous and following assessment. If a previous and following assessment is not available, this assessment will not be used for any calculation.

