4.1.2 Treatment phase

Patient eligibility will be checked once all screening procedures are completed. An eligibility review and confirmation will be embedded in the Interactive Response Technology (IRT) system. Please refer to and comply with detailed guidelines in the IRT manual.

Subjects may continue study treatment until disease progression, occurrence of unacceptable toxicity, withdrawal of consent by the patient, patient is lost to follow-up, or the sponsor terminates the study.

Dose adjustment (reduction, interruption or dose re-escalation) according to safety findings will be allowed. Regular safety reviews by an IDMC will be performed.

Tumor assessments will be performed every 8 weeks (+/- 1 week) starting from the first date of study treatment, and as clinically indicated, until the first 12 months of treatment are complete, or disease progression. Following 12 months if no disease progression, tumor assessments will occur every 12 weeks (+/- 2 weeks), and as clinically indicated until disease progression. Scans could be obtained earlier if there is concern of disease progression. If additional tumor assessments are performed prior to starting further anticancer therapy, the corresponding tumor assessments should also be sent for central review. Additional evaluation should be performed to confirm response at least 4 weeks after it was first observed.

Every 28 days will be considered one cycle. All the medications will be given with food. Clinical visits will be twice a cycle for the 1st two cycles, then once a cycle from there on.

The therapy on clinical trial will continue until disease progression (radiological), or intolerable adverse effects, or patient wishes to withdraw consent.

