9.4 Data management and quality control

Novartis personnel (or designated CRO) will review the data entered by investigational staff for completeness and accuracy. Electronic data queries stating the nature of the problem and requesting clarification will be created for discrepancies and missing values and sent to the

investigational site via the EDC system. Designated investigator site staff is required to respond promptly to queries and to make any necessary changes to the data.

Concomitant treatments and prior medications entered into the database will be coded using the WHO Drug Reference List, which employs the Anatomical Therapeutic Chemical classification system. Medical history/current medical conditions and adverse events will be coded using the Medical dictionary for regulatory activities (MedDRA) terminology.

Samples and/or data collected for all third party data such as ECG, PK [REDACTED] will be processed centrally and the results will be sent electronically to Novartis (or a designated CRO).

The occurrence of any protocol violations will be determined. After these actions have been completed and the data has been verified to be complete and accurate, the database will be declared locked and data made available for data analysis. Authorization is required prior to making any database changes to locked data, by joint written agreement between Novartis and the CRO biostatistician and database management.

After database lock, the investigator will receive a CD-ROM or paper copies of the patient data for archiving at the investigational site.

10 Statistical methods and data analysis

Data will be analyzed by Novartis and/or designated CRO. Any data analysis carried out independently by the investigator must be submitted to Novartis before publication or presentation.

It is planned that the data from participating centers in this protocol will be combined, so that an adequate number of patients will be available for analysis. Data will be summarized with respect to demographic and baseline characteristics, efficacy and safety observations and measurements using descriptive statistics (quantitative data) and contingency tables (qualitative data).

The study data will be analyzed and reported based on all patients' data up to the time when all patients have potentially completed at least six cycles of treatment or discontinued the study.

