3.5.2.2 Phase II

- Clinical Benefit Rate (CBR):

Clinical Benefit Rate (CBR) is defined as the proportion of patients with a complete response (CR), partial response (PR), stable disease (SD) or Non-CR Non-PD (NCRNPD) at 24 weeks as per RECIST V1.1. Thus, any instance of CR, PR, SD or NCRNPD in the first 24 weeks of the treatment, without having an instance of progressive disease (PD) will be accounted for, while calculating CBR. The instances of unconfirmed CR and/or PR will also be accounted for, while calculating CBR.

Demonstration of significant Clinical Benefit Rate (CBR) will be based on this study with at least an 80% power to test the null hypothesis that the clinical benefit rate in 24 weeks is at least 10% or less with an alternative hypothesis that this rate is above 10%.

All the other patients will be counted as not having clinical benefit.

The study is designed to test the following statistical hypothesis:

$$H_0 : \text{CBR} \leq 10\% \text{ vs. } H_1 : \text{CBR} > 10\%$$

The null hypothesis will be rejected and successful clinical benefit will be demonstrated if the lower limit of the 95% confidence interval is greater than at least 0.10. Thus, if 8 or more patients show clinical benefit at 24 weeks then the null hypothesis will be rejected and significant clinical benefit will be demonstrated.

To show significant clinical benefit, currently at least ≥ 8 patients will have to achieve CBR at 24 weeks. But if the number of patients enrolled in the study is higher than the planned number of 33 patients (approximately 44 to 46), then the requirement for the number of patients to have achieved CBR will also increase (up to ≥ 10 patients).

CBR will be summarized by frequency and percentage together with the 95% confidence intervals. An exact binomial confidence interval (implemented using SAS procedure FREQ with EXACT statement for one-way tables) will be calculated [Clopper & Pearson, 1934].

CBR will be calculated based on FAS; however, patients with only non-measurable disease at baseline will be included in the numerator if they achieved a complete response.

For primary efficacy variable, the analysis time point is when all patients who are enrolled complete 24 weeks or discontinue from the study earlier. Phase 1 patients who had received the RP2D and are post CDK 4/6 completing 24 weeks or discontinue early will also be included in the final phase II analysis.

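### A documented progression whose scan month is missing would be discarded rather than dated, because a progression scan usually has no following assessment

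*Protocol*

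**What the plan says.** Protocol 14.2.35 (Appendix 2) has four steps.

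- Complete dates are required: "All investigation dates (e.g. X-ray, CT scan) must be completed with day, month and year".
- Partly dated assessments are kept: "If one or more investigation dates are incomplete but other investigation dates are available, this/these incomplete date(s) are not considered", and the assessment date is then derived as in 14.2.25.
- If every date lacks only the day, the first of the month is used.
- If the month is missing, "the respective assessment will be considered to be at the date which is exactly between previous and following assessment". Then: "If a previous and following assessment is not available, this assessment will not be used for any calculation".

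Protocol 14.2.28 calls this block guidance, but 14.2.33 introduces it as the rules for programming efficacy results, and SAP 3.3.1 refers to Appendix 2 for details. The SAP has no rule of its own for scan dates. Its section 6.1 covers study drug, adverse event and concomitant medication dates and marks other imputations as not applicable. SAP 3.7.3 says missing data for secondary efficacy are not imputed, and SAP section 5 lists no change from the protocol.

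On scheduling, Protocol 4.1.2 says that after 12 months "tumor assessments will occur every 12 weeks (+/- 2 weeks), and as clinically indicated until disease progression"; the 8-weekly scans before that also end at progression. Protocol 7.1.7 continues efficacy follow-up only for patients who stop treatment for a reason other than progression.

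**The concern.** The midpoint needs a scan on each side. A mid-course SD scan has both, so it survives a missing month. A progression scan normally has only a previous one, so the same recording defect removes it. An assessment can therefore be lost because it is the terminal one, and terminal scans are often the progression scans.

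At stake are the PFS event and, in a narrower set of cases, the Phase II primary endpoint. SAP 3.5.2.2 counts a patient who has any CR, PR, SD or non-CR/non-PD in the first 24 weeks and "without having an instance of progressive disease (PD) will be accounted for, while calculating CBR". If the PD record is out of all calculations, that condition can be met by a patient who progressed.

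**Working it through.** **Step 1: apply the rule.** Take SD at Week 8 and PD at Week 16, with no usable month on any Week 16 investigation and no later scan.

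- *Strict reading (either neighbour missing):* the Week 16 assessment is dropped.
- *Lenient reading (both neighbours missing):* it is kept, but no midpoint can be computed and no other date is prescribed.

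Neither reading handles the case.

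**Step 2: PFS.** With the PD dropped, SAP 3.7.2.2 censors at the last adequate assessment, here Week 8. If the PD was the first post-baseline scan, Protocol 14.2.34 gives a duration of 1 day. A later death is still an event by definition. However, the Table 14-7 defaults censor a death that follows two or more missing assessments, and censor at the last adequate assessment once new anticancer therapy is given.

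**Step 3: CBR.**

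| Definition | SD at Week 8, PD at Week 16 dropped |
|---|---|
| Protocol Table 3-2 (status at 24 weeks) | No Week 24 status, so not a benefit |
| SAP 3.5.2.2 (any SD or better in 24 weeks, no PD) | Counts as benefit |

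Under the SAP wording, nothing changes if the PD was the first scan (no earlier SD or better) or fell after Week 24.

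**Step 4: other terminal scans.** A final Week 24 SD scan without a month is dropped too. Under Table 3-2 that loses a benefit, and PFS is censored earlier. A dropped confirmatory PR scan loses a confirmed response, since SAP 3.3.1.6 requires two determinations at least 4 weeks apart.

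**Step 5: the decision boundary.** The criterion is a lower 95% Clopper-Pearson limit above 0.10. For r of n, the lower limit is the 2.5% quantile of Beta(r, n − r + 1). The SAP plans 33 patients per group with a bar of 8. It reports 46 recruited to Group 1 and allows the bar to rise to as many as 10.

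| r/n | Lower limit | Exact one-sided error at p = 0.10 |
|---|---|---|
| 7/33 | 0.0898 | 0.0417 |
| 8/33 | 0.1109 | 0.0141 |
| 9/46 | 0.0936 | 0.0364 |
| 10/46 | 0.1095 | 0.0140 |

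One misclassified patient changes a group's result only if the true count is one below the bar.

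**Step 6: how often.** The documents give no rate. Assume a share q of terminal PD scans has no month on any investigation, a share f of 25–50% of non-benefit patients has an earlier SD or better, and the true CBR is 10%. Under the SAP wording:

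- expected patients wrongly counted = n × 0.9 × f × q
- effective rate = 0.10 + 0.9 × f × q

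For n = 33 and a bar of 8:

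| q | Expected number | Error (0.0141 without the rule) |
|---|---|---|
| 0.1% | 0.007–0.015 | 0.0143–0.0145 |
| 1% | 33 × 0.9 × 0.25 × 0.01 = 0.07 to 33 × 0.9 × 0.50 × 0.01 = 0.15 | 0.016–0.018 |
| 5% | 0.37–0.74 | 0.025–0.042 |

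For n = 46 and a bar of 10, q = 1% gives 0.10–0.21 patients and an error of 0.016–0.019. The effect is negligible unless missing months are common.

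**The case against.** The trigger is narrow. Full dates are mandatory, and Protocol 9.4 adds that "Electronic data queries stating the nature of the problem and requesting clarification will be created for discrepancies and missing values". Protocol 14.2.9 records the actual date of each scan, and 7.2.1.1 sends all study imaging to the imaging CRO within 2 weeks. A PD scan is also not always the last: management follows the local read, so a PD called only centrally may be followed by more scans, and Protocol 7.1.2 lets some patients stay on study after progression. PFS is a descriptive secondary endpoint with no test. All of this stands, and it is why the point is minor.

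Three stronger readings are tempting and not supported.

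- *Every error favours the regimen.* The rule does not look at the response, and a lost final SD or PR can count against the regimen (Step 4).
- *Progression is generally erased from PFS and CBR.* It is lost only when no usable month exists. The CBR effect needs the SAP wording, PD by Week 24 and an earlier non-PD response.
- *The section flatly contradicts itself.* The month rule applies when the month is not completed for any of the investigations. Read as one scan lacking a month, this conflicts with the preceding paragraph. Read as none having a month, it follows on from it. The wording is ambiguous, not plainly contradictory.

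What remains is that, when the rule does fire on a final PD, it discards a known outcome because its date is imprecise, and no other text rescues it.

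**Conclusion.** The point holds as a minor edge case. Under 14.2.35 as written, a documented PD with no usable month and no following scan is removed or left undatable. A PFS event then becomes censoring at the last adequate assessment unless a death counts. Under SAP 3.5.2.2 alone, a patient who progressed by Week 24 after an earlier CR, PR, SD or non-CR/non-PD counts as benefit.

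No material bias can be shown, because the frequency is not given and is probably very low. The what-if figures rest on assumed values of q and f. A group's decision is exposed only at its boundary, such as 7 versus 8 of 33. The reason to act is that the rule gives a wrong result when it fires and is almost free to correct.

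**What to change.** In Protocol 14.2.35, or as an override in the SAP:

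1. Apply the month-missing rule only when no investigation at that assessment has a usable month. Otherwise use the complete dates as in 14.2.25.
2. State that an assessment with a documented response is never discarded solely because its month is missing.
3. In particular, keep a documented PD as a PFS event and as PD for CBR. Give it a pre-specified date bounded by the previous assessment and the next known date, such as the end-of-treatment visit, start of new therapy, death or last contact. The midpoint of those bounds is one workable convention; what matters is that it is fixed before database lock.
4. Repeat the rule in the SAP, so that SAP 3.7.3 and section 6.1 no longer leave scan dates uncovered.

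The cost is a few sentences and a few lines of programming. In an open-label trial, settling it after results are seen would be a post-hoc choice.

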14.2.36 Incomplete dates for last known date patient alive or death

All dates must be completed with day, month and year. If the day is missing, the 15th of the month will be used for incomplete death dates or dates of last contact.

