2.1.1.9 Last contact date

The last contact date will be derived for patients not known to be dead at the analysis cut-off using the last complete date among the following:

- All assessment dates (e.g. vital signs assessment, performance status). Note, only a true on study assessment date or patient contact date will be used. If there is a visit date without evidence of any actual assessment performed that date will not be used. No dates post cut-off will be used.
- Medication dates including study medications, concomitant medications, and anti-neoplastic therapies administered after study treatment discontinuation (with non-missing medication/procedure term).
- Adverse event dates (with non-missing verbatim AE term present).

- Last known date patient alive collected on the ‘Survival information’ eCRF.
- Date of discontinuation from end of treatment page and ‘End of post-treatment follow-up’ eCRF.

The last contact date is defined as the latest complete date from the above list or the cut-off date whichever comes first. The cut-off date will not be used for last contact date, unless an actual assessment or patient contact was performed.

Important note: imputed dates (e.g. the analysis cut-off date programmatically imputed to replace the missing end date of a dose administration record) will not be used to derive the last contact date, except for the following: partial date’s imputation is allowed to be used for event (death) and for censoring date only if coming from Survival Information page.

The last contact date will be used for censoring of patients in the analysis of overall survival.

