3.7.2.2 PFS, ORR, OS and DOR

- PFS:

Progression-free survival (PFS) is defined as the time from date of treatment to the date of first documented progression or death due to any cause. For PFS, a patient who didn't have the event at the date the analysis data cut-off will be censored at the time of the last adequate assessment, prior to data cut-off. PFS will be assessed based on the responses provided by the Investigator on centrally assessed data. The PFS will be analyzed using FAS.

PFS will be analyzed using the Kaplan-Meier Product-Limit method. Estimates of the 25th, median and 75th percentile of the PFS and their 95% confidence intervals will be provided, if applicable. Additionally, above analysis will be repeated on the locally assessed tumor response. Analysis will also be performed using per protocol analysis set, as appropriate.

- ORR:

Overall response rate (ORR) defined as the proportion of patients who's best overall response is either complete response (CR) or partial response (PR) according to RECIST 1.1. ORR will be calculated based on FAS; however, patients with only non-measurable disease at baseline will be included in the numerator if they achieved a complete response. ORR will be summarized by frequency and percentage. The exact 95% two-sided confidence interval will also be provided.

When examining overall response, patients with a best overall response assessment of unknown (UNK) will not be regarded as "responders" but may be included in the denominator for ORR calculation.

Best overall response for each patient will be listed and summarized on FAS.

- OS:

Overall survival (OS) is defined as the time from date of first treatment to the date of death due to any cause. If a patient is not known to have died, survival will be censored at the last date of contact.

OS will also be summarized by Kaplan-Meier Product-Limit method based on FAS. Estimates of the 25th, median and 75th percentile of the PFS and their 95% confidence intervals will be provided, if applicable.

- DOR:

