6.1 Imputation rules

6.1.1 Study drug

In the calculation of treatment exposure duration, if a dosing record has either a missing end date (for the last record for that treatment component) or an end date after the cut-off date, the cut-off date will be used as the end date. Such imputed data will be flagged in the listings. Where a date is recorded as a partial date, the missing day will be imputed as follows:

Start date: The day will be imputed by the 15th of the month. If day and month are missing day and month will be imputed by July 1st of the year. If there is a record indicating that the dose record started earlier, the start date will be imputed by the end date of the previous record + 1 day. In case the imputed start date is later than the complete end date, the record will not be considered for analysis.

End date: The day will be imputed by the 15th of the month, and if day and month are missing then by July 1st of the year. If there is a record indicating that this started later, the end date will be imputed by the start date of the next record - 1 day. In case the imputed end date is earlier than the complete start date, the record will not be considered for analysis.

Imputed DAR start and end dates will be flagged in the listings.

The protocol allows for continuous dosing record entry with start dates and end dates for all compounds of study treatment. A separate dosing record should be entered whenever there is a

change in the dosing which can be due to dose change, delay or missed doses. If the start date and end date is on the same date then that DAR record will be called single dose DAR record.

For dates known to be within the trial period, the last known contact date will be used if this imputation makes the date later than the last known contact date but within the trial completion date. If the imputed date is earlier than the first medication date, the first medication date will be used.

For dates prior to the treatment start, the treatment start date will be used if this imputation makes the date later than the treatment start date.

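### A death date with a missing day is set to the 15th without checking when the patient was last seen alive, so a patient seen later that month is dated dead before a documented contact

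*Protocol*

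**What the plan says.** Protocol 14.2.36 first requires complete dates ("All dates must be completed with day, month and year") and then gives the fallback: "If the day is missing, the 15th of the month will be used for incomplete death dates or dates of last contact". The fallback carries no condition.

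SAP 2.1.1.9 generally bars imputed dates from the last contact derivation but makes an exception for partial dates: "imputation is allowed to be used for event (death) and for censoring date only if coming from Survival Information page". It sets no lower limit for an imputed death. It also derives a last contact date only for survivors: "The last contact date will be derived for patients not known to be dead at the analysis cut-off". A patient who has died therefore has no such variable to compare with.

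OS and PFS both depend on this date. In SAP 3.7.2.2, "Overall survival (OS) is defined as the time from date of first treatment to the date of death due to any cause", and PFS runs to "the date of first documented progression or death due to any cause". Under Protocol 14.2.34, duration is end date minus start date plus one day, and the same section says that time-to-event variables cannot be negative.

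SAP 3.7.3 says that missing data for the secondary efficacy analyses are not imputed at all, which does not agree with either rule above.

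**The concern.** The rule looks only at the month of death. If a visit, scan or phone contact took place after the 15th of that month, the analysis file holds a death that precedes evidence of life. OS is then too short for that patient. PFS is too short as well when death is the first event, or when a progression scan after the 15th is overtaken by the imputed death. Time to definitive ECOG deterioration (SAP 3.7.2.5) also counts death as an event and is exposed in the same way.

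Elsewhere the SAP does tie imputed dates to known ones. Dosing dates are held to the first medication date (6.1.1), and AE and concomitant medication end dates to the date of death (6.1.2.2 and 6.1.3.2). An impossible order of dates is therefore unlikely to be intended.

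**Working it through.** The plan gives no figure that depends on this rule, so there is nothing to reproduce. The checks apply the stated rule to dates.

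**Is there a lower limit anywhere?** The only last-contact check among the SAP imputation rules is in 6.1.1, Study drug: "the last known contact date will be used if this imputation makes the date later than the last known contact date". That is a cap: it pulls late dates back. The lower limit in the same section is the first medication date, again for dosing records. SAP 6.1.3.5 (other imputations) is marked not applicable, and SAP section 5 lists no change to the protocol analyses. No lower limit for death dates was found.

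**One patient.** Start 10 January 2018, last seen 20 August, died 25 August, day not recorded.
- Current rule: death on 15 August, OS = 218 days.
- OS at the last contact: 223 days. True OS: 228 days.
- The imputed death falls 20 - 15 = 5 days before the contact, and OS is 10 days too short.

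For a contact on day d > 15, the imputed death is d - 15 days too early relative to that contact: 1 day for d = 16, up to 16 days for d = 31.

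**Negative OS.** Start on the 20th, death on the 28th of the same month, day missing: 15 - 20 + 1 = -4 days; the true value is 28 - 20 + 1 = 9. A start on the 16th gives 0, and any later start gives a negative value.

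**All missing-day deaths.** With the day of death uniform over the month, the mean of (15 - day) is +0.5, -0.5 and -1.0 day for months of 28, 30 and 31 days. Deaths before the 15th are dated late and offset those dated early.

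**Share affected.** Assumptions: 30-day month, day of death uniform on 1 to 30, gap from last contact to death uniform on 0 to G whole days. With m = day of death - 15 (1 to 15), a death is misordered when the gap is less than m. For G of 14 or more there are 1 + 2 + ... + 15 = 120 such pairs out of 30(G + 1). For G = 7 there are 92 out of 240. These pairs carry 680 days (G of 14 or more) or 596 days (G = 7) between imputed death and last contact. Moving the imputed death up to the last contact recovers exactly those days, never passes the true date, and so raises the mean error and lowers the mean absolute error by the same amount. Before the change these are -0.5 and 7.5 days.

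| G (days) | Share dated before last contact | Days recovered per missing-day death | Mean error after | Mean absolute error after |
|---|---|---|---|---|
| 7 | 92/240 = 38% | 596/240 = 2.48 | +2.0 | 5.0 |
| 14 | 120/450 = 27% | 680/450 = 1.51 | +1.0 | 6.0 |
| 28 | 120/870 = 14% | 680/870 = 0.78 | +0.3 | 6.7 |
| 56 | 120/1710 = 7% | 680/1710 = 0.40 | -0.1 | 7.1 |
| 168 | 120/5070 = 2% | 680/5070 = 0.13 | -0.4 | 7.4 |

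G = 28 corresponds to one visit per cycle, 56 to the 8-week efficacy follow-up (Protocol 7.1.7), and 168 to the 24-week survival contact (Protocol 7.1.8).

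**The case against.** The 15th is a midpoint rule and is close to unbiased overall. A reader might infer that the plan shortens OS and PFS in general; the near-zero mean error above shows that it does not. The high shares need contact within one or two weeks of death. On the contact intervals that the protocol sets after treatment ends, they drop to 7% and 2%, and only of deaths that lack a day. Complete dates are required, Protocol 9.4 provides queries for missing values and discrepancies, and Appendix 2 is a general guideline whose programs must be adapted to each study (14.2.38). OS and PFS are secondary Kaplan-Meier summaries without a test, and the primary CBR rests on tumor response.

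All of this stands, and it sets the size of the point. It does not supply the missing check. A query may not recover the day, and adapting programs is not a pre-specified rule for an event date.

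A further objection concerns the remedy. A lower limit corrects only deaths dated too early and leaves early-month deaths dated late, so the mean error can rise. That is true when contact is close to death, and it is the price of records in a possible order.

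**Conclusion.** The point holds as a small gap in the date rules. As written, they can date a death 1 to 16 days before a documented contact and can give an OS that Protocol 14.2.34 excludes. The shortening is confined to patients with a missing day of death who were seen after the 15th of that month; for PFS the imputed death must also become the first event. The documents do not support a claim of general downward bias or of any effect on the primary result.

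The 38% to 2% range rests on the assumed uniform day of death and uniform gap to last contact. The total effect cannot be stated, because the number of death dates without a day is not given.

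**What to change.** In Protocol 14.2.36 and SAP 2.1.1.9 write: *If the day of death is missing, use the later of the 15th of that month and the latest complete date on which the patient is documented alive (including the treatment start date).* The sources listed in SAP 2.1.1.9 can be reused for deceased patients, taking complete, non-imputed dates only. Add that SAP 3.7.3 does not override this rule.

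Do not add a day to the lower limit: a patient can die on the day of last contact. Under the 0 to 7 day assumption, a limit one day later would give a mean error of +2.4 and a mean absolute error of 4.7 days, against +2.0 and 5.0 for the rule proposed here. No matching rule is needed for partial last-alive dates, because SAP 2.1.1.9 already takes the latest complete date.

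The cost is one sentence in each document, a clarification in SAP 3.7.3, and a line of code. The downside is the upward shift in mean error shown in the table when contact is close to death.
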